5 STUDY OBJECTIVES

5.1 PRIMARY

- To evaluate the efficacy, safety and tolerability of alemtuzumab (IV) in paediatric patients from 10 to <18 years of age with RRMS who have disease activity on prior DMT.

5.2 SECONDARY

- To assess the pharmacokinetics (PK), pharmacodynamics (PD), antidrug antibody (ADA) formation, and potential effects of alemtuzumab on other MS disease characteristics such as cognition and quality of life.

6 STUDY DESIGN

6.1 DESCRIPTION OF THE STUDY

This is an open-label, rater-blinded, single-arm, before and after switch study of efficacy, safety and tolerability of alemtuzumab in paediatric patients from 10 to <18 years of age with RRMS with disease activity on prior DMT.

The study will consist of:

- **Screening period** (0-28 days prior to M-4) - Patients and parents will receive information on the study and on alemtuzumab. Inclusion/exclusion criteria will be reviewed. After informed consent signature, screening assessments for eligibility will be performed. Screening assessments may require more than one visit within the screening period which may last a maximum of 28 days.
- **Prior DMT phase (approximately 4 months): M-4 to M0**
 - **Eligibility confirmation visit:** At the end of the screening period (at M-4) patients/parents will come to the site to confirm patient is eligible for the study. Investigator will check that all assessment allow patient inclusion. During this visit patients will be reminded to continue their prior DMT (limited to interferon or GA only).
 - **From M-4 visit to D-14 to D-7:** Phone calls (approximately every month) will be done, to remind patients to continue on their DMT and check patient status.
 - **Day -14 to D-7 visit:** Investigator will confirm patient is eligible for alemtuzumab administration and will tell the patient to discontinue current DMT 7 days prior to administration of first dose of alemtuzumab at Month 0.
- **Alemtuzumab treatment phase** (approximately 2 years) – This phase starts with administration of first dose of alemtuzumab at M0, after discontinuation of current DMT, and ends at M24. The second dose of alemtuzumab will be administered at M12. The MRI based primary efficacy endpoint will be assessed over a 4 month period during this phase compared to an equal period during the prior DMT phase.

Note: end of treatment phase (EOTP) refers to the end of the alemtuzumab treatment phase (see graphic study design [[Section 1.1](#)]).
- **Safety monitoring phase** (approximately 3 years) – Additional safety follow-up and monitoring for all patients treated with alemtuzumab will be conducted during this phase to yield a total of 5 years of follow-up since first alemtuzumab treatment, including 4 years post last treatment with alemtuzumab.

Note: end of study (EOS) refers to the end of the safety monitoring phase (see graphic study design [[Section 1.1](#)]).

In addition, and for the primary endpoint assessment, two periods have been defined:

- **Period 1:** will occur from M-4 up to M0. A baseline MRI will be performed close to M-4 during the screening period and another at Visit 3. Both MRI will be taken while patients are on their prior DMT. It is important to ensure that these 2 MRI assessments are performed 4 months (± 7 days) apart.
- **Period 2:** will occur from M4 to M8: The MRI performed at the M4 visit will be the baseline MRI for Period 2. A second MRI will be performed after alemtuzumab first course of treatment at M8. It is important to ensure that these 2 MRI assessments are performed 4 months (± 7 days) apart.

These two periods will be compared for the primary endpoint analysis.

6.2 DURATION OF STUDY PARTICIPATION

6.2.1 Duration of study participation for each patient

The maximum study duration per patient will be approximately 5 years and 5 months:

- **Screening period:** 0-28 days prior to M-4 from signed informed consent to eligibility confirmation.
- **Prior DMT phase:** approximately 4 months from signed informed consent and screening qualification to prior DMT discontinuation. **Alemtuzumab treatment phase:** approximately 2 years, from first dose alemtuzumab administration to one year after last dose of alemtuzumab administration.
- **Safety monitoring phase:** approximately 3 years to complete the 48 months safety follow-up post last treatment with alemtuzumab.

6.2.2 Determination of end of clinical trial (all patients)

The EOS is defined as being the “last patient last visit” planned with the protocol. The last patient visit will be considered when the last patient has completed safety monitoring phase (M60). The Sponsor reserves the right to discontinue the study at any time.

6.3 INTERIM ANALYSIS

A partial database lock will be done after the last patient has completed efficacy assessments including MRI at the end of Period 2. This database lock will allow comparing lesion counts between Period 1 (M-4 to M0) and Period 2 (M4-M8). No formal interim analysis will be performed.

6.4 STUDY COMMITTEE

6.4.1 Scientific advisory committee:

The scientific advisory committee (SAC) is composed of field experts and Sponsor-based scientists with clinical and methodological expertise. This Committee, led by a Chairperson, is selected by the Sponsor for advice regarding scientific issues and operational conduct of the study. The SAC will also review any amendments, and provide input regarding interpretation of study results.

Among its responsibilities, the SAC will receive study status reports from the Sponsor, and will review the recommendations from the data monitoring committee (DMC) throughout the study.

Moreover, the SAC will be responsible for the primary publication(s) emanating from the study. The Principal Investigator (PI) of the study will be selected by the Sponsor and will be the first author for the primary publication(s). PIs at the 3 sites enrolling the most patients will also be included as authors for the primary publication, in addition to the other SAC members.

Detailed activities and responsibilities of the SAC are provided in the SAC charter.

6.4.2 Data monitoring committee

A DMC, operating independently from the Sponsor and Clinical Investigators, will be responsible for overseeing the safety of patients and the risk/benefit ratio throughout the study.

This committee is composed of externally-based individuals with expertise in the disease under study, biostatistics and/or clinical research. The primary responsibilities of the DMC are to ensure the patients welfare as well as to evaluate and review the safety and other applicable data throughout the course of the study and make appropriate recommendations to the Sponsor regarding the conduct of the clinical trial. The specific responsibilities of the DMC will be described in the DMC charter.

7 SELECTION OF PATIENTS

7.1 INCLUSION CRITERIA

I 01. Patients with RRMS aged from 10 years to less than 18 years at study entry are eligible. Patients must meet the criteria of diagnosis of MS as defined by the International Paediatric Multiple Sclerosis Study Group criteria for paediatric MS (12) and the criteria of MS based on McDonald criteria 2010 (18) (Appendix C).

Specific to the Russian Federation:

In the Russian Federation: Patients with RRMS aged ≥ 12 years to < 18 years are eligible at study entry (Appendix H).

I 02. Signed written informed consent/assent obtained from patient and patient's legal representative (parent or guardian) according to local regulations.

I 03. Expanded Disability Status Scale (EDSS) score of 0.0 to 5.0 (inclusive) at screening (Appendix D).

I 04. At least 2 recorded MS attacks, and at least 1 MS attack (relapse) in the last year during treatment with an IFNB or GA after having been on that therapy for at least 6 months, and is currently still taking the same therapy.

I 05. At least 1 of the following:

- ≥ 1 new or enlarging T2 hyperintense lesion or gadolinium enhancing lesion while on that same prior therapy (IFNB or GA), OR
- 2 or more relapses in the prior year, OR
- tried at least 2 MS DMTs.

7.2 EXCLUSION CRITERIA

Patients who have met all the above inclusion criteria listed in Section 7.1 will be screened for the following exclusion criteria which are sorted and numbered in the following 3 subsections:

NOTE: Prior to initiation of any alemtuzumab treatment course, contraindications should be reviewed as pre-treatment verification of eligibility.

7.2.1 Exclusion criteria related to study methodology

E 01. Any progressive or nonrelapsing forms of MS.

E 02. Conditions/situations such as:

- Impossibility to meet specific protocol requirements,
- Current participation in another interventional clinical study. If a patient has been enrolled in a clinical trial and treated with a comparator agent that is an approved agent

for screening inclusion (INF or GA), they may be considered for this trial if they meet all inclusion and exclusion criteria otherwise,

- Patient is the Investigator or any SubInvestigator, research assistant, pharmacist, study coordinator, other staff or relative thereof directly involved in the conduct of the protocol,
- Uncooperative patient or any condition that could make the patient potentially noncompliant to the study procedures in the opinion of the Investigator.

E 03. Mental condition rendering the patient or parent/guardian unable to understand the nature, scope, and possible consequences of the study.

E 04. Clinically relevant cardiovascular, hepatic, neurological, endocrine, or other major systemic disease making implementation of the protocol or interpretation of the study results difficult or that would put the patient at risk by participating in the study in the opinion of the Investigator.

E 05. History of drug or alcohol abuse.

E 06. History of known HIV positivity.

7.2.2 Exclusion criteria related to alemtuzumab and/or mandatory background therapies

E 07. Pregnant or breast-feeding female patients or those who plan to become pregnant during the study.

E 08. Unwilling to agree to use a highly effective contraceptive method as defined ([Appendix A](#)) when receiving a course of alemtuzumab treatment and for 4 months following that course of treatment (fertile patients only).

E 09. Female patients who have commenced menstruating (ie, are of childbearing potential) and are unwilling or unable to be tested for pregnancy.

E 10. Previous treatment with alemtuzumab.

E 11. Treatment with natalizumab, daclizumab, fingolimod, methotrexate, azathioprine, cyclosporine, or mycophenolate mofetil in the last 6 months prior to screening, or as determined by the treating physician to have residual immune suppression from these or other MS treatments.

E 12. Treatment with teriflunomide in the last 12 months except if the patient underwent the accelerated elimination procedure as per local teriflunomide label.

E 13. Previous treatment with mitoxantrone, cyclophosphamide, cladribine, rituximab, ocrelizumab, leflunomide, or any cytotoxic therapy.

E 14. Previous treatment with any investigational medication (drug that has not been approved at any dose or for any indication). Use of an investigational medication that was subsequently licensed and nonstandard use of a licensed medication (eg, using a dose other than the dose

that is stated in the licensed product labeling or using a licensed therapy for an alternative indication) is not exclusionary. Prior treatment with herbal medications or nutritional supplements is also permitted.

E 15. Intolerance of pulsed corticosteroids, especially a history of steroid psychosis.

7.2.3 Exclusion criteria related to the current knowledge of alemtuzumab and study methodology

If a patient was deemed a screen failure, he or she may be re-screened for this study up to 2 times. If a patient who previously failed screening for any reason is re-screened, the patient must sign a new informed consent form and be assigned a new patient number by IWRS/IVRS (the next sequential patient number at the site). All screening assessments need to be repeated to confirm eligibility for the study. Rescreening assessments may be discussed with the Sponsor on a case-by-case basis.

Medical History

E 16. History of malignancy.

E 17. Prior documented history of thrombocytopenia, or platelet count at screening < lower limit of normal (LLN).

E 18. Any disability acquired from trauma or another illness that, in the opinion of the Investigator, could interfere with evaluation of disability due to MS.

E 19. Patients with known Type 1 hypersensitivity or anaphylactic reactions to the active substances or any of the excipients, or intolerance of acyclovir or its therapeutic equivalent.

Medical Conditions

E 20. Major systemic disease or other illness that would, in the opinion of the Investigator, compromise patient safety or interfere with the interpretation of study results, eg, current peptic ulcer disease, or other conditions that may predispose to hemorrhage, immune cytopenias, rheumatoid arthritis, systemic lupus erythematosus, other connective tissue disorders, vasculitis, inflammatory bowel disease, severe psoriasis.

E 21. Medical, psychiatric, cognitive, or other conditions that, in the Investigator's opinion, compromise the patient's ability to understand the patient information, to give informed consent, to comply with the trial protocol, or to complete the study.

E 22. Major psychiatric disorder that is not adequately controlled by treatment in the opinion of the Investigator.

E 23. Epileptic seizures that are not adequately controlled by treatment.

- E 24. MRI-related conditions: conditions that could interfere with MRI acquisition and/or interpretation of MRI results (eg, claustrophobia, orthopedic implants/treatments, orthodontic treatments etc).
- E 25. Known bleeding disorder (eg, dysfibrinogenemia, factor IX deficiency, hemophilia, Von Willebrand's disease, disseminated intravascular coagulation, fibrinogen deficiency, clotting factor deficiency).

Infections

- E 26. Prior history of invasive fungal infections.
- E 27. Active infection, eg, deep-tissue infection, that the Investigator considers sufficiently serious to preclude study participation.
- E 28. In the Investigator's opinion, patient is at high risk for infection (eg, indwelling catheter, dysphagia with aspiration, decubitus ulcer, history of prior aspiration pneumonia or recurrent urinary tract infection).
- E 29. Infection with hepatitis B, C viruses (positive serology, but not due to hepatitis immunization).
- E 30. History of tuberculosis (TB)/latent TB (unless it is documented by a specialist that the patient has been adequately treated and can now start treatment with a biologic agent).
- E 31. Testing will be conducted for human papillomavirus (HPV) infection as and when recommended by local public health authorities. If the testing is positive, the patient may be eligible after the condition has resolved as per the Investigator opinion (eg, follow-up HPV test is negative or cervical abnormality has been effectively treated).
- E 32. Any other illness or infection (latent or active) that, in the Investigator's opinion, could be exacerbated by study medication.

Laboratory Parameters

- E 33. Confirmed platelet count <LLN of the evaluating laboratory at Screening or documented at <100 000/ μ L within the past year on a sample without platelet clumping.
- E 34. CD4+, CD8+, or CD19+ (ie, absolute CD3+CD4+, CD3+CD8+, or CD19+/ mm^3) count <LLN at Screening; if abnormal cell count(s) return to within normal limits, eligibility may be reassessed.
- E 35. Absolute neutrophil count <LLN at Screening; if abnormal cell count returns to within normal limits, eligibility may be reassessed.

Note: If the treating physician suspects out-of-range cell count results are based upon issues of sample transportation or environmental conditions, the treating physician may request a repeat sample to be evaluated locally to confirm the patient is not excluded from the trial. If out-of-range cell counts are not confirmed through evaluations performed locally, the treating physician should

document (in source data and in a CRF comment) that the central laboratory results are considered falsely exclusive, and proceed to enroll the patient.

- E 36. Any hepatic or renal function value Grade 2 or higher at Screening, with the exception of hyperbilirubinemia due to Gilbert's syndrome, unless, in the Investigator's opinion, the abnormality is due to a condition that has resolved (eg, recent interferon treatment subsequently discontinued) and levels return to within normal limits. See [Table 7](#) below, drawn from the National Cancer Institute (NCI) Common Terminology Criteria for Adverse Events v3.0 (CTCAE), published 09 August 2006.

Table 7 - Common terminology criteria for adverse events v3.0, published 09 August 2006.

Hepatic	
Bilirubin	>1.5 x ULN
SGOT/AST	>2.5 x ULN
SGPT/ALT	>2.5 x ULN
Alkaline phosphatase	>2.5 x ULN
Renal	
Creatinine	>1.5 x ULN

Abbreviations: AST: aspartate aminotransferase; ALT: alanine aminotransferase; SGOT: serum glutamic oxaloacetic transaminase; SGPT: serum glutamic-pyruvic transaminase; ULN: upper limit of normal.

8 STUDY TREATMENTS

8.1 INVESTIGATIONAL MEDICINAL PRODUCT(S)

Name of the Investigational Medicinal Product (IMP):

Alemtuzumab.

Pharmaceutical form:

Concentrate for solution for infusion (sterile concentrate). Each vial contains 12 mg/1.2 mL of solution.

Dose of drug per administration:

First course: at Month 0 for 5 consecutive days

Calculation of the dose used will be determined based on patient weight taken at the first infusion visit, of the first course, during the physical examination:

- For patients ≥ 50 kg: 12 mg/day.
- For patients < 50 kg: 0.24 mg/kg/day.

Second course: at Month 12 for 3 consecutive days

Calculation of the dose used will be determined based on patient weight taken at the first infusion visit, of the second course, during the physical examination:

- For patients ≥ 50 kg: 12 mg/day.
- For patients < 50 kg: 0.24 mg/kg/day.

Route of administration:

IV infusion.

8.1.1 Administration

Alemtuzumab will be administered only after a decision from the Study Investigator.

First course: Alemtuzumab will be administered by IV infusions for 5 consecutive days at Month 0 in a supervised medical setting at a dose of:

- For patients ≥ 50 kg: 12 mg/day.
- For patients < 50 kg: 0.24 mg/kg/day.

Second Course will occur 12 months after the first course.

Second Course: Alemtuzumab will be administered by IV infusion for 3 consecutive days at Month 12 in a supervised medical setting at a dose of:

- For patients ≥ 50 kg: 12 mg/day.
- For patients < 50 kg: 0.24 mg/kg/day (this equates to 12 mg/day for a 50 kg patient).

8.1.1.1 Method of preparation at the clinical site

Alemtuzumab must be diluted before infusion. The diluted solution must be administered by IV infusion. The infusion duration will be approximately 4 hours starting within 8 hours after dilution. Extend the duration of the infusion if clinically indicated.

Additional requirements for alemtuzumab infusion and monitoring during and post infusion are specified in [Section 10.1.4](#) Visit 4/M0/D1 (first course of alemtuzumab) and [Section 10.1.10](#) Visit 16/M12 (second course of alemtuzumab).

8.1.1.2 Special precautions for disposal and other handling

The vial contents must be inspected for particulate matter and discoloration prior to administration. Do not use if particulate matter is present or the concentrate is discolored. Do not shake the vials prior to use.

For IV administration, withdraw the prescribed amount of alemtuzumab from the vial into a syringe using aseptic technique. Inject into 100 mL of sodium chloride 9 mg/mL (0.9%) solution for infusion or glucose (5%) solution for infusion. This medicinal product must not be diluted with other solvents. The bag must be inverted gently to mix the solution.

Alemtuzumab contains no antimicrobial preservatives and, therefore, care must be taken to ensure the sterility of the prepared solution. It is recommended that the diluted product be administered immediately. Each vial is intended for single use only.

Any partially used, unused, or damaged drug vials should be disposed of in accordance with local requirements.

8.2 NONINVESTIGATIONAL MEDICINAL PRODUCTS

A) Premedications:

- Day -1 (day before first IV infusion at each course) in the morning:
 - Oral prednisone/prednisolone 1 mg/kg or 50 mg one dose, whichever is lower, or equivalent,
 - H2 antagonist according to the local label (eg, ranitidine).

- Day -1 (day before first IV infusion at each course) in the evening:
 - H1 antagonist according to the local label (eg, cetirizine),
 - H2 antagonist according to the local label (eg, ranitidine).
- On days of IV infusions (1 hour prior to infusion):
 - H2 antagonist: eg, ranitidine or equivalent,
 - NSAID/antipyretic: paracetamol or equivalent,
 - H1 antagonist IV diphenhydramine (25 mg or appropriate weight based dosing based on local health authority recommendations [[Appendix H](#)]), immediately followed by:
 - IV methylprednisolone: administer 1000 mg on infusion Days 1, 2, 3 (all courses) and ≥ 500 mg on infusion Days 4 and 5 (if 5 days of infusion).

Notes:

- a) If diphenhydramine IV is not available, an equivalent H1 antagonist can be used at an equivalent dosing, via IV route,
 - b) If no H1 antagonist is available in IV formulation, an oral formulation of an equivalent compound can be used at an equivalent dosing, 2 hours prior to infusion.
- Day 4 and Day 5 of the first course:
 - H1 antagonist, H2 antagonist, and antipyretics as needed,
 - Fluid intake will be encouraged.

B) Concomitant medications:

- Acyclovir 200 mg oral twice daily (or therapeutic equivalent) will also be provided/given at the beginning on the first day of each treatment course and continuing for a minimum of 1 month following treatment with alemtuzumab.

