
Non Investigational medicinal product(s)
 
Formulation:
	
Premedications:
 
 • Day -1 (day before first IV infusion at each course) in the morning: 
 - Oral prednisone/prednisolone, 1 mg/kg or 50 mg one dose, whichever is lower or equivalent, - H2 antagonist according to the local label (eg, ranitidine). • Day -1 (day before first IV infusion at each course) in the evening: 
 - H1 antagonist according to the local label (eg, cetirizine), - H2 antagonist according to the local label (eg, ranitidine). • On days of IV infusions (1 hour prior to infusion): 
 - H2 antagonist: eg, ranitidine or equivalent, - NSAID/antipyretic: Paracetamol or equivalent, - H1 antagonist IV diphenhydramine (25 mg or appropriate weight based dosing based on local health authority recommendation), immediately followed by: 
 - IV methylprednisolone: administer 30 mg/kg or 1000 mg (whichever is lower) on infusion Days 1, 2, 3 (all courses) and ≥ 500 mg on infusion Days 4 and 5 (if 5 days of infusion). • Notes: 
 a) If diphenhydramine IV is not available, an equivalent H1 antagonist can be used at an equivalent dosing, via IV route. b) If no H1 antagonist is available in IV formulation, an oral formulation of an equivalent compound can be used at an equivalent dosing, 2 hours prior to infusion. • Day 4 and Day 5 of the first course: 
 - H1 antagonist, H2 antagonist, and antipyretics as needed, - Fluid intake will be encouraged. 
Concomitant medications:
 
 • Acyclovir 200 mg oral twice daily (or therapeutic equivalent) will also be provided at the beginning on the first day of each

	treatment course and continuing for a minimum of 1 month following treatment with alemtuzumab.
Route(s) of administration:	Methylprednisolone: IV Acyclovir: Oral Prednisone/Prednisolone: Oral Long-acting, nonsedating, nonselective antihistamine: Oral and/or IV H2-receptor antagonist: Oral
Dose regimen:	See above

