10.1.4 Visit 4/M0/D1 (first course of alemtuzumab)

Alemtuzumab treatment must be initiated and supervised by a neurologist experienced in the treatment of patients with MS. Specialists and equipment required for the timely diagnosis and management of the most frequent adverse reactions, especially autoimmune conditions and infections, must be available.

During the alemtuzumab infusion days, patients are not required to stay hospitalized overnight; however it remains at Investigator's discretion to decide if patient needs to be hospitalized during infusion periods.

Observation for infusion reactions is recommended during and for at least 2 hours (based on local requirements) after alemtuzumab infusion.

The day prior to first alemtuzumab administration patient should take the premedication as specified in [Section 1.2.1](#) and [Section 8.2](#).

On days of alemtuzumab infusion, and 1 hour prior to the infusion, H1 antagonist IV should be administered immediately followed by 1000mg IV methylprednisolone (whichever is lower), on the first 3 days of alemtuzumab administration and ≥ 500 mg on infusion Days 4 and 5. H2 antagonist medications and NSAID/antipyretic should be administered on the 5 days of alemtuzumab administration as needed. Study patients should also receive antiviral prophylaxis for herpetic viral infection beginning on Day 1 and continuing for a minimum of 1 month. If diphenhydramine IV is not available, an equivalent H1 antagonist can be used at an equivalent dosing, via IV route. If no H1 antagonist is available in IV formulation, an oral formulation of an equivalent compound can be used at an equivalent dosing, 2 hours prior to infusion.

Alemtuzumab will be administered as daily IV infusion on 5 consecutive days in a supervised medical setting. Calculation of the dose used will be based on patient weight. Vital signs during infusion days will be monitored.

The following assessments should be done as listed in the study flow chart (refer to [Section 1.2.1](#)):

- Physical examination and vital signs.
- Check for compliance.
- Preinfusion blood samples collection for clinical laboratory assessments and for ADA.
- Blood sample collection for serum creatinine and ALT.
- Blood samples collection for immune markers (optional) and PK.
- AE/SAE will be monitored (if any).
- Concomitant medication will be checked and reported (if any).
- The Investigator or designee will contact the IVRS to obtain a treatment kit number.

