10.1.10 Visit 16/M12 (second course of alemtuzumab)

Visit 16 (M12) can occur within -7 days or +30 days of the scheduled visit.

The following assessments should be done as listed in the study flow chart:

- Physical examination and vital signs.
- Perform Tanner staging.
- Blood and urine samples collection for clinical laboratory assessments including pregnancy test (for females of childbearing potential), thyroid function test, urinalysis and for ADA.
- Blood samples collection for lymphocyte phenotyping.
- Blood samples collection for PK and immune markers (optional).
- Assess and confirm eligibility for alemtuzumab administration.
- Alemtuzumab will be administered as daily IV infusion on 3 consecutive days in a supervised medical setting. Calculation of the dose used will be based on patient weight. Observation for infusion reactions is recommended during and for at least 2 hours (based on local requirements) after alemtuzumab infusion.
- The Investigator or designee will contact the IVRS to obtain a treatment kit number.
- On days of Alemtuzumab infusion, and 1 hour prior to the infusion, H1 antagonist IV should be administered immediately followed by 30mg/kg or 1000mg IV methylprednisolone (whichever is lower). H2 antagonist medications and NSAID/antipyretic should be administered on the 3 consecutive days of alemtuzumab

administration as needed. Study patients should also receive antiviral prophylaxis for herpetic viral infection beginning on Day 1 and continuing for a minimum of 1 month. If diphenhydramine IV is not available, an equivalent H1 antagonist can be used at an equivalent dosing, via IV route. If no H1 antagonist is available in IV formulation, an oral formulation of an equivalent compound can be used at an equivalent dosing, 2 hours prior to infusion.

- Vital signs during infusion days will be monitored.
- AE/SAE will be monitored (if any).
- Concomitant medication will be checked and reported (if any).

The following infusion management procedures must be utilized for each infusion and each treatment course:

- Pre-infusion :

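### The Day 1–3 IV methylprednisolone dose is stated inconsistently for both alemtuzumab courses; the readings diverge for patients below 33.3 kg

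*Protocol*

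**What the plan says.** Four places in the current protocol text give the IV methylprednisolone dose for infusion Days 1–3.

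- **Clinical Trial Summary, non-investigational products (all courses):** "IV methylprednisolone: administer 30 mg/kg or 1000 mg (whichever is lower) on infusion Days 1, 2, 3 (all courses").
- **Section 8.2 (all courses):** "IV methylprednisolone: administer 1000 mg on infusion Days 1, 2, 3 (all courses").
- **Section 10.1.4 (course 1, Month 0):** "immediately followed by 1000mg IV methylprednisolone (whichever is lower), on the first 3 days of alemtuzumab administration".
- **Section 10.1.10 (course 2, Month 12):** "immediately followed by 30mg/kg or 1000mg IV methylprednisolone (whichever is lower").

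For Days 4 and 5 of the first course, the Summary, Section 8.2 and Section 10.1.4 agree on at least 500 mg. Section 8.2 also lists the oral steroid for the day before infusion, and there the dose is limited by weight: "Oral prednisone/prednisolone 1 mg/kg or 50 mg one dose, whichever is lower, or equivalent".

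Section 8.1.1.1 states: "Additional requirements for alemtuzumab infusion and monitoring during and post infusion are specified in" Sections 10.1.4 and 10.1.10. For premedication on the day before infusion, Sections 10.1.3, 10.1.4 and 10.1.9 refer to Section 8.2.

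**The concern.** The Summary and Section 8.2 both claim to cover every course, yet one limits the dose by weight and the other does not. That alone is a direct conflict for each course. The visit sections do not settle it. Section 10.1.10 sides with the Summary for course 2. Section 10.1.4 cannot be followed as written, because a dose cannot be the lower of one value.

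This is a dosing instruction for children, so it has to be settled in the protocol. A site working from Section 8.2 gives an uncapped dose in both courses. A site working from the two visit sections meets an incomplete rule in course 1 and a capped rule in course 2. A child of low weight could therefore receive different steroid doses depending on the site, or on the course at the same site, and each dose could be defended from some part of the text. Compliance with the premedication rule would then have no fixed standard. Section 4 makes methylprednisolone part of the regimen in order to reduce infusion-associated reactions, and those reactions are themselves assessed as safety events (Section 9.3.1).

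**Working it through.** **Inputs.** The capped rule (Summary, Section 10.1.10) gives min(30 mg/kg × weight, 1000 mg) per day. The flat rule (Section 8.2) gives 1000 mg per day. Both courses include infusion Days 1–3, so each has three days at issue. Eligibility starts at 10 years (12 in the Russian Federation) with no minimum weight (Section 7.1). The protocol foresees light patients, because it reduces the alemtuzumab dose below 50 kg (Sections 4 and 8.1). It gives no weight distribution, so the weights below are assumptions for illustration.

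**Where the rules separate.** The cap binds when 30 × weight < 1000, that is, below 1000/30 = 33.3 kg. At or above that weight both rules give 1000 mg. This includes every patient between 33.3 and 50 kg, even though their alemtuzumab dose is reduced.

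**Size of the difference.** The excess is 1000 − 30 × weight per day. Multiply by 3 for one course, and by 6 for both courses if weight is unchanged and the flat rule is used each time.

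| Assumed weight | Capped dose/day | Flat dose/day | Excess/day | Flat dose per kg | Excess, one course | Excess, both courses |
|---|---|---|---|---|---|---|
| 25 kg | 25 × 30 = 750 mg | 1000 mg | 250 mg (250/750 = 33%) | 40.0 mg/kg | 750 mg | 1500 mg |
| 30 kg | 30 × 30 = 900 mg | 1000 mg | 100 mg (100/900 = 11%) | 33.3 mg/kg | 300 mg | 600 mg |
| 33 kg | 33 × 30 = 990 mg | 1000 mg | 10 mg (10/990 = 1%) | 30.3 mg/kg | 30 mg | 60 mg |
| 33.3 kg or more | 1000 mg | 1000 mg | 0 | at most 30.0 mg/kg | 0 | 0 |

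**Difference between courses in one child.** Suppose a site reads Section 10.1.4 as a flat 1000 mg and then follows Section 10.1.10. A child who stays at 25 kg receives 3 × 1000 = 3000 mg over Days 1–3 of course 1 and 3 × 750 = 2250 mg in course 2.

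**Days 4–5.** The 500 mg floor exceeds 30 mg/kg only below 500/30 = 16.7 kg, so it does not conflict with a 30 mg/kg limit at any weight in the table.

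**Which reading was intended.** The Summary carries the same Days 4–5 text as Section 8.2 and still keeps the 30 mg/kg limit, so the two lists differ on the Day 1–3 methylprednisolone dose and not on the Day 4–5 dose. The leftover words in Section 10.1.4 only make sense if a weight-based alternative once stood beside the 1000 mg. Both points favour the capped rule, but neither proves it.

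**The case against.** The conflict in the text is not in dispute. The strongest case on the other side concerns its weight and the direction of the correction.

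**Practical reach.** Nothing changes at 33.3 kg or above, the affected group may be empty, no harm is shown and the primary analysis is untouched. The two-course totals assume constant weight in a growing child, and they assume a flat dose in course 2 although that course's own visit section states the cap. All of this is true and limits the size of the point. It does not remove a contradiction in a live paediatric dosing rule.

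**Intent.** The history of Amended Protocol 02 records a methylprednisolone update for Section 8.2 and a halved dose on Days 4 and 5 for Section 10.1.4, but only the H1-antagonist change for Section 10.1.10. On that reading the flat dose could be the newer wording, and 500 mg as half of 1000 mg fits it. However, the history never records removal of the 30 mg/kg limit, and the Summary holds the cap together with the Days 4–5 text. The history does not decide the question, so clinical confirmation is needed.

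**Days 4–5.** If those days were meant as half the Day 1–3 dose, then under the cap half would be 375 mg at 25 kg and 450 mg at 30 kg, both below the 500 mg floor. This is worth asking when the rule is confirmed. The operative text states a floor, not a half dose, and it is consistent wherever it appears.

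**Cross-references.** The pointer in Section 8.1.1.1 concerns alemtuzumab infusion and monitoring, not steroids by name, and the explicit premedication pointers go to Section 8.2. Section 8.2 also contains other flat doses, so the weight limit on the oral steroid is only mild support. Both remarks are fair. The conflict between the Summary and Section 8.2 stands without either argument.

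**Conclusion.** The concern holds. The Day 1–3 IV methylprednisolone dose is contradictory for both courses, incomplete in Section 10.1.4, and left without a rule of precedence. Following Section 8.2 exactly gives a child below 33.3 kg more steroid than the Summary and Section 10.1.10 allow. At assumed weights of 30 and 25 kg the excess is 100 and 250 mg per day (11% and 33%), or 300 and 750 mg per course. Over two courses it would be 600 and 1500 mg if weight did not change and the flat rule were applied throughout.

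The number of patients concerned cannot be worked out from the protocol and may be zero. The protocol does not call 30 mg/kg a toxicity limit, so no specific harm is asserted. Sample size and the primary MRI comparison are unaffected. The point should be corrected because it is a plain error in a dosing instruction and is cheap to remove.

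**What to change.** Ask the sponsor's clinical team to confirm the intended Day 1–3 rule. If it is the capped one, as the text suggests, state the lower of 30 mg/kg and 1000 mg in Sections 8.2 and 10.1.4, matching the Summary and Section 10.1.10. If a flat 1000 mg is intended, the Summary and Section 10.1.10 must change instead, and the stray comparison must come out of Section 10.1.4. At the same time, confirm that the 500 mg floor on Days 4–5 is meant to apply at low body weight. That text already agrees across the protocol and can otherwise stay.

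The cost is a wording correction in two sections at the next amendment and a notice to sites. It adds no patients, visits or procedures.
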